Immunosuppressant therapy will be per the individual center's usual treatment protocol. Immunosuppressant levels will be done and immunosuppressant dosages will be recorded on treatment days 3 and 7; weekly during the treatment period; at the end of treatment; and 4, 12 and 24 weeks after discontinuation of therapy. Unscheduled therapeutic drug levels may be obtained more frequently at the discretion of the investigator. Modifications in immunosuppression regimen will be at the discretion of the investigator.

Efficacy. Serial quantitative HCV RNA testing will be performed by day 7 after transplant if study medication has not been started, Day 1, on treatment weeks 1 and 4; end of treatment; and weeks 4, 12 and 24 after discontinuation of therapy.

Safety. Adverse events (AEs) will be recorded for all patients who receive a NAT-positive HCV organ through 4 weeks after the last dose of study drug. Serious adverse events (SAEs) will be reported to the lead investigators and the independent data and safety monitor within 24 hours of recognition by study staff. SAEs will be collected for the entire duration of the study. After the 10th study subject has reached treatment week 4, the lead investigators and the independent data and safety monitor will conduct a safety and efficacy review of all safety and efficacy data to date. When these same subjects reach follow up week 12 (corresponding to 24 weeks after starting study drug), the lead investigators and the independent data and safety monitor will conduct another safety and efficacy review.

Virologic Failure Substudy. In the event of virologic failure following treatment with SOF/VEL, subjects will be eligible for re-treatment with 12 weeks of sofosbuvir/velpatasvir/voxilaprevir (SOF/VEL/VOX) VOSEVI therapy in the Virologic

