- Laboratory tests including serum blood urea nitrogen, creatinine, estimated glomerular filtration rate, sodium, potassium, bicarbonate, ALT, AST, alkaline phosphatase, total bilirubin, albumin, hemoglobin, INR, and immunosuppressant level;
- Serum or urine hCG for females of childbearing potential at Follow Up Week 4;
- Hepatitis B surface antigen at Follow Up Week 4;
- Quantitative HCV RNA;
- Concomitant medications of interest including immunosuppressant on follow up week 4;
- Immunosuppressant dose;
- Assessment for AEs on Follow Up Week 4.

Early End of Treatment or Treatment Failure visit

This unscheduled visit will occur if the subject discontinues study drug prior to planned end of treatment for any reason OR the subject has been determined to have viral breakthrough or relapse. This visit must occur within 2 weeks of stopping treatment or recognition of viral breakthrough or relapse. Each visit is anticipated to require 30 minutes of the subject's time. The following events will take place:

- Clinical examination;
- Laboratory tests including serum blood urea nitrogen, creatinine, estimated glomerular filtration rate, INR, sodium, potassium, bicarbonate, ALT, AST, alkaline phosphatase, total bilirubin, albumin, hemoglobin, and immunosuppressant level;
- Quantitative HCV RNA and HCV genotype;
- Testing for HCV resistance associated substitutions;
- Concomitant medications of interest including immunosuppressant;
- Assessment for AEs.

Visit Windows

The study visit windows are +/- 2 days for the day 3 visit, +/- 4 days for the weekly on treatment visits and end of treatment visit, and +/- 10 days for the follow up visits

End of Study Definition

End of study is considered to be completion of the Follow Up Week 24 Visit. Subjects who enter the Virologic Failure Substudy will also follow an additional

Schedule of Assessments for the Virologic Failure Substudy (See Appendix 3a).

Sample Storage

Residual biological samples will be frozen and stored at the individual study sites. No

human genetic testing will be performed without express consent of the study subjects. At the conclusion of this study, these samples may be retained in storage per individual institution policy.

Study Visits for Virologic Failure Substudy

Study visits for the Virologic Failure Substudy may coincide with visits for the main study. When this occurs, laboratory assessments for the main study may also be used for the Virologic Failure Substudy.

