A serious adverse event (SAE) is defined as an event that results in the following:

- Death;
- Life threatening event in which the subject was at risk of death at the time of the event;
- Inpatient hospitalization or prolongation of existing hospitalization;
- Persistent or significant disability/incapacity;
- A congenital anomaly/birth defect;
- A medically important event or reaction that may jeopardize the subject or may require intervention to prevent one of the other outcomes constituting SAEs.

Safety monitoring

Safety data will be collected for all subjects who sign their confirmation of consent at the end of the consent form and undergo a NAT-positive transplant through 4 weeks after the last dose of study drug. The Principal Investigators will continuously monitor the study for safety. An independent data and safety monitor will act in an advisory capacity to monitor participant safety and data quality, as well as to evaluate the progress of the study.

The lead investigators will be responsible for holding periodic meetings to update the study group regarding enrollment, study conduct, and potential safety issues that may affect subjects' decisions about enrolling or continuing study drug throughout the study, including, but not limited to: AEs, SAEs, and new treatments that come available.

Clinical Laboratory Abnormalities. Laboratory abnormalities without clinical significance are not recorded as AEs or SAEs. However, laboratory abnormalities that require medical or surgical intervention or lead to investigational medicinal product interruption or discontinuation must be recorded as an AE, as well an SAE, if applicable. In addition, laboratory assessments that are associated with signs and/or symptoms must be recorded as an AE, or SAE, if applicable. If the laboratory abnormality is part of a syndrome, record the diagnosis (i.e. anemia), not the laboratory abnormality (i.e. decreased hemoglobin).

Adverse Events. The investigator, or sub-investigator, is responsible for assessing AEs and SAEs for causality and severity. AEs will be graded using the Common Terminology Criteria for Adverse Events (CTCAE) Version 4.03. This grading scale can be found at https://evs.nci.nih.gov/ftp1/CTCAE/CTCAE_4.03_2010-06-14_QuickReference_8.5x11.pdf.

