For AEs associated with laboratory abnormalities, the event should be graded on the clinical severity in the context of the underlying conditions. All AEs, regardless of cause or relationship, must be collected and reported in the eCRF database as instructed.

SAEs will be collected for the duration of the study. SAEs related to study drug, graft loss, or death will be reported to the lead investigators and the independent data and safety monitor within 24 hours of recognition by study staff. Stable chronic conditions that are present prior to the Pre-Transplant Day and do not worsen during the treatment period and safety follow up period are not considered adverse events.

Safety Review. When the first 10 study subjects reach treatment week 4, the lead investigators and the independent data and safety monitor will conduct a safety and efficacy review. When these subjects reach follow up week 12 (24 weeks after starting study drug), the lead investigators and the independent data and safety monitor will conduct another safety and efficacy review.

Early termination: Participants may withdraw their consent to participate in this study at any time after they sign informed consent. Principal investigators can terminate participant(s) from the study for safety concerns. Subjects who take at least one dose of study drug and do not complete the planned 12 weeks of treatment will come for an early end of treatment visit.

STATISTICAL CONSIDERATIONS

Analysis Objectives

The primary objective of this study is to determine the efficacy of SOF/VEL in viral eradication among HCV negative liver and/or kidney transplant recipients with HCV NAT positive donors.

The secondary objective of this study is to determine the safety and tolerability of all SOF/VEL among HCV negative liver and/or kidney transplant recipients with HCV NAT positive donors.

The exploratory objective of this study is to compare the observed waiting time for transplant for HCV negative liver and/or kidney transplant recipients with HCV NAT positive donors to the expected waiting time for transplant with HCV negative donors at the participating centers.

Primary Efficacy Endpoint

The proportion of participants with SVR 12 defined as HCV RNA < lower limit of quantification 12 weeks after last dose of antiviral therapy.

Secondary Endpoints:

- Proportion of subjects with SVR24 defined as HCV RNA < lower limit of quantification 24 weeks after last dose of antiviral therapy;

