- Proportion of subjects with viral relapse defined as HCV RNA <LLOQ at end of treatment with subsequent quantifiable HCV RNA;
- Proportion of participants with on-treatment virologic breakthrough defined as > 1 log increase in viral RNA after treatment week 1;
- Proportion of subjects who prematurely discontinue antiviral therapy before the planned end of treatment;
- Patient and graft survival at 6 months post-transplant.

Exploratory Endpoint

Change in wait time for kidney and/or liver transplant based on UNOS data for the participating regions.

Analysis Sets

The primary analysis set for safety and efficacy analyses includes all subjects who undergo liver and/or kidney transplant after signing Part 2 of the Informed Consent. Treatment-emergent data will be analyzed and defined as data collected from the first dose of study drug through the date of the last dose of study drug plus 30 days.

Data Handling Conventions

Missing data will not be imputed other than for quantitative HCV PCR. If a quantitative PCR is missing, the value will be imputed as LLOQ if the viral load before and after are both LLOQ.

Efficacy Analysis

Primary and Secondary Endpoints

No formal hypothesis testing will be performed, as this is an exploratory study. No inferential statistics or statistical comparisons are planned for efficacy endpoints. All subjects who undergo liver and/or kidney transplant with a nucleic acid test positive organ will be included in the analysis. We assume that none of the subjects will achieve SVR 12 without any antiviral therapy. The existing data for SOF/VEL have demonstrated a SVR rate above 94% in non-cirrhotic patients. We anticipate a similar SVR rate for our study. Along with the percentage of patients with SVR12, a two-sided 95% confidence interval (CI) is constructed by using the Clopper-Pearson method. With a sample size of 30 patients, if the SVR12 rate is 90%, the lower bound of the 95% CI would be 79% and the upper bound of the 95% CI would be 100%.

Exploratory Endpoint

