Shorter wait time from listing to transplant is a potential benefit of accepting a HCV positive organ. To characterize wait time among HCV positive organ recipients, mean wait time in log₁₀ days will be calculated separately for liver and kidney transplant recipients. With a sample size of 10, 15, or 20 patients per HCV positive organ type and a standard deviation of 1 log₁₀ days of wait time, we have 80% power to obtain a two-sided 95% CI half-width of 8, 5, and 4 days, respectively (CI half-width of 0.9, 0.7, and 0.6 log₁₀ days).

To explore wait time by acceptance of HCV positive versus negative organs, wait time would be collected for the HCV positive organ recipient and the next HCV negative organ recipient at the transplant center, matched on blood type, gender, and transplant MELD (+/-5) for liver recipients and KDPI (+/- 0.25) for kidney recipients. Mean wait time in log₁₀ days for a HCV positive versus negative organ would be compared separately among liver and kidney recipients. We anticipate obtaining wait time on 60 transplant recipients (at least 20 liver and 20 kidney recipients). For a two-sided paired t-test assuming an alpha level of 0.05, we estimate having 80% power to detect a mean difference in wait time of 20, 10, and 8 days for sample sizes of 20, 30, and 40 patients, respectively.

Safety Analysis

Safety will be assessed during the study through the reporting of AEs and by clinical laboratory tests at various time points during the study. Concomitant medication usage will also be assessed throughout the study. Descriptive statistics on the number and types of AEs will be recorded and presented in a tabular format. Treatment-emergent AEs (TEAEs) will also be summarized by relationship to study drug and severity. In addition, TEAEs leading to premature discontinuation of the study drug will be summarized and listed. Liver or kidney grade 3 or 4 laboratory abnormalities will be described in the narrative.

Independent Data and Safety Monitor (IDSM)

An IDSM with relevant clinical expertise will be chosen who has no financial, scientific,

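### Treatment-emergent data are defined by collection date alone, with no onset-or-worsening test against Day 1, and the window ends 2 days after non-serious AE collection does

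*Combined protocol and SAP*

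**What the plan says.** All of this is in the combined protocol and SAP.

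- **Analysis Sets** (Statistical Considerations): "Treatment-emergent data will be analyzed and defined as data collected from the first dose of study drug", running "through the date of the last dose of study drug plus 30 days". No criterion of onset or worsening follows.
- **Study Design, Safety paragraph**: "Adverse events (AEs) will be recorded for all patients who receive a NAT-positive HCV organ through 4 weeks after the last dose" of study drug. **Safety monitoring** repeats this end point for those who sign the confirmation of consent and "undergo a NAT-positive transplant through 4 weeks after the last dose of study drug". Serious AEs are collected for the whole study.
- **Adverse Events paragraph**: conditions not counted as AEs are "Stable chronic conditions that are present prior to the Pre-Transplant Day and do not worsen" during treatment and safety follow-up. The **Definitions** paragraph treats a pre-existing event as an AE if it worsens or changes in nature while the subject is in the study.
- **Safety Analysis**: treatment-emergent AEs (TEAEs) are summarised by relationship to study drug and by severity. For laboratory data, "Liver or kidney grade 3 or 4 laboratory abnormalities will be described in the narrative".
- **Treatment Regimen**: drug normally begins in the first week after transplant, with up to 4 weeks allowed.
- **Visit Windows**: plus or minus "10 days for the follow up visits".

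**The concern.** A treatment-emergent label normally means that something began, or got worse, after the first dose. Here it means only that the data were collected after the first dose. In most trials the difference is small. In this one the drug is started shortly after major surgery, when complications and abnormal liver or kidney values are to be expected. The protocol's own Pharmacologic considerations paragraph names acute kidney insufficiency after transplant as a concern for early SOF/VEL use, and at least 10 of up to 30 subjects are to be kidney recipients.

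Safety is the secondary objective and there is no control arm against which to read the surgical background. If carried-over events sit in the same TEAE and severity tables as new ones, those tables are harder to interpret. The independent data and safety monitor is asked to weigh the nature, frequency and severity of AEs. The first review comes when 10 subjects reach treatment week 4, which is at most 4 + 4 = 8 weeks after transplant.

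**Working it through.** No sample size or power figure is involved. The check sets the rules side by side and does the day arithmetic.

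**1. Reference point of each rule.**
- Analysis Sets: collected on or after the first dose. Onset and change in grade play no part.
- Definitions: worsening during study participation, which begins before surgery.
- Adverse Events: stable chronic conditions present before the Pre-Transplant Day, also before surgery.
- Treatment Regimen: up to 4 × 7 = 28 days may lie between transplant and first dose.

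Take a complication that begins in those 28 days and is still present at the first dose. It is not a stable chronic condition from before the Pre-Transplant Day, so the exclusion does not remove it. If it is collected after the first dose, it meets the treatment-emergent definition. If it was entered before the first dose, it does not. The same event is classified by its date of entry.

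**2. When such an event would be collected.** The main-study Day 1 visit text lists laboratory tests and concomitant medications but no AE assessment. The first on-treatment visit that lists one is Day 3, with a window of ± 2 days, so Day 1 to Day 5. First collection after dosing is therefore possible. It is not proven: the main schedule table in Appendix 3 could not be read in the text available. In the substudy, the Appendix 3a table appears to mark a Day 1 AE assessment that the matching visit text omits, so silence in the text is weak evidence.

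**3. Laboratory values.** Clinical Evaluations schedules the panel on treatment days 1, 3 and 7 and then weekly. A Day 1 value therefore exists, but no analysis names it as baseline. The grade 3 or 4 narrative makes no comparison with it, so nothing requires a value improving from a worse Day 1 result to be told apart from a new one. Abnormalities without clinical significance are not recorded as AEs, so they receive no AE causality assessment either.

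**4. End of the window.**
- Treatment-emergent window: 84 + 30 = day 114.
- Non-serious AE collection: 84 + 4 × 7 = day 112.
- Gap: 114 − 112 = 2 days; 2/114 = 1.8%.
- Follow-up week 4 visit: 28 − 10 = 18 to 28 + 10 = 38 days after last dose. If AEs were ascertained only at that visit, on day v, the uncovered part would be max(0, 30 − v): 12 days at v = 18, 2 days at v = 28, and 0 from v = 30.

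**5. Size of the effect at the start of the window.** This needs the share of subjects with an ongoing event, or a grade 3 or 4 liver or kidney value, at Day 1. The documents do not give it, so no count of misclassified subjects can be derived.

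**The case against.** The best defence is that labelling is not attribution. A reader might infer that surgical events will be ascribed to SOF/VEL. The documents do not support that: the investigator assesses causality for every AE, and TEAEs are tabulated by relationship. Nor does the rule hide a drug effect outright; it mixes events together. This part of the defence stands for AEs. It does not cover the unsplit TEAE count, or laboratory values that never become AEs.

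A second defence is that complications between transplant and Day 1 should already be on record before dosing, and so fall outside the window on its literal wording. That is a fair reading, and it is why the point is that such events can be misclassified, not that they will be. It still leaves the classification hanging on the date of entry.

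Third, a reader might infer inflated grade 3 or 4 laboratory rates, or put a number on the subjects affected, for example 20% to 60% of 30, that is 6 to 18. Neither is supported. The plan has a narrative and no treatment-emergent laboratory rate, and nothing in the documents backs that range. A narrative could also mention the Day 1 value, though the plan does not require it.

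Fourth, a reader might infer that 12 of 114 days (10.5%) go unobserved for non-serious AEs. That takes the earliest permitted visit as the end of collection. The protocol sets collection by time since last dose, and a visit on day 30 or later leaves no gap.

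Finally, new surgical complications arising after Day 1 would still be TEAEs under any onset rule. That is true, and for those the causality assessment and the independent safety review remain the safeguard.

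**Conclusion.** The point holds in a limited form. The definition has no onset or worsening test and no Day 1 reference, and neither of the two rules on pre-existing conditions supplies one. Pre-drug complications collected after dosing, and grade 3 or 4 liver or kidney values already present or improving at Day 1, are not reliably separated from new ones. The outputs exposed are the overall TEAE and severity summaries and the laboratory narrative. Attribution to SOF/VEL and the efficacy endpoints are not affected.

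The size of this cannot be stated from the documents. The end-date mismatch can: a nominal 2 days, non-serious AEs only. The conclusion assumes that AE recording starts at transplant, which is the natural reading of the collection rule, and that some events of the transplant-to-Day-1 interval are still ongoing or first collected after dosing. The change should be made because it is cheap and makes single-arm safety tables readable, but no planned test depends on it.

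**What to change.** Amend Analysis Sets and Safety Analysis as follows.

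- Define a TEAE as an AE with onset, or increase in CTCAE grade, on or after the first dose relative to the last pre-dose status, up to the end of the window.
- Report grade 3 or 4 liver and kidney laboratory abnormalities as treatment-emergent when they are at least a one-grade increase from the Day 1 pre-dose value. Show those already present at Day 1 separately with their later course, since a value at the top grade cannot rise further.
- List AEs from transplant to Day 1 separately.
- Use one end date, in days, for non-serious AE collection and for the treatment-emergent window.

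The cost is SAP wording and a little programming. No new laboratory tests are needed, because the Day 1 panel is already scheduled; the text should confirm that it is drawn before the first dose. The downside is reliance on recorded AE onset dates, so the case report form must capture onset relative to the first dose. The documents do not say whether it does.

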The primary efficacy endpoint is the proportion of subjects who achieve a sustained virologic response (SVR12). Secondary endpoints include proportion of subjects who achieve SVR24, the proportion of subjects with viral relapse or viral breakthrough and patient and graft survival at Week 36 (24 weeks after starting study drug).

Safety:

Safety will be assessed through the reporting of adverse events and clinical laboratory tests

When the first 10 subjects reach treatment week 4, the lead investigators and the independent data and safety monitor will conduct a Safety Review. When these same subjects reach follow up week 12 (24 weeks after starting study drug), the lead investigators and the independent data and safety monitor will conduct another Safety Review.

Statistical Methods:

Sample size was selected to provide safety and efficacy data. The small size of the pilot study does not permit hypothesis testing. Descriptive statistics on the number and types of AEs will be recorded and presented.

Safety Analysis:

Safety analysis will include summaries of AEs and laboratory evaluations

BACKGROUND AND SCIENTIFIC RATIONALE

In the United States, the number of patients listed for solid organ transplant dramatically exceeds the numbers of organs available and utilized for donation. For kidney transplant, mean waiting times are measured in years. There is a 4 % mortality on the kidney wait list, with much higher rates for diabetic and elderly candidates. On the liver wait list, the mortality rate is considerably higher, averaging about 20% at most centers. Numerous strategies are utilized to expand the standard donor pool for kidney or liver transplant, including using organs from deceased donors exposed to chronic viral infections (e.g. cytomegalovirus and hepatitis B virus), Public Health Services increased risk donors, older donors, donation after cardiac death, and livers with increased steatosis.

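### The 79% to 100% interval given for SVR12 at 90% in 30 patients is not the Clopper-Pearson interval the plan specifies, which is 73.5% to 97.9%

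*Combined protocol and SAP*

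**What the plan says.** The Efficacy Analysis section (Primary and Secondary Endpoints) of the combined protocol and SAP says that, alongside the SVR12 percentage, "a two-sided 95% confidence interval (CI) is constructed by using the Clopper-Pearson method". The next sentence illustrates this at the planned size: "With a sample size of 30 patients, if the SVR12 rate is 90%, the lower bound of the 95% CI would be 79" percent, and "the upper bound of the 95% CI would be 100" percent.

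The same paragraph gives the expected result: "The existing data for SOF/VEL have demonstrated a SVR rate above 94% in non-cirrhotic patients. We anticipate a similar SVR rate for our study". It also says "No inferential statistics or statistical comparisons are planned for efficacy endpoints". On the choice of 30 patients, the synopsis says only: "Sample size was selected to provide safety and efficacy data. The small size of the pilot study does not permit hypothesis testing". The documents give no other precision or power figure for SVR12.

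**The concern.** The method is named in one sentence and the example in the next does not fit it. An upper limit of 100% is the visible sign. With 3 failures among 30 patients, a Clopper-Pearson upper limit must lie below 100%, because a true rate of 100% could not produce any failures.

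With no efficacy test planned, the confidence interval is the only statement of uncertainty for the primary endpoint. A reader who takes the example at face value would conclude that 27 responders in 30 rule out a true SVR12 below 79%. By the specified method they rule out only rates below about 73.5%. In terms of failure, the compatible rate runs up to about 26.5% (100 − 73.5), not 21% (100 − 79). Recipients in this trial are HCV negative and receive a viremic organ, and the consent discussion lists graft loss, cirrhosis and death among the consequences of unsuccessful treatment. The upper end of the plausible failure rate should therefore be stated correctly.

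**Working it through.** **Inputs, all from the Efficacy Analysis section.** n = 30; observed rate 90%, so x = 0.90 × 30 = 27 responders, a whole number; two-sided 95%, α = 0.05; method Clopper-Pearson. No outside assumption is needed.

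**Step 1: reproduce the plan's figure.** The Wald interval is p ± 1.96 × √(p(1 − p)/n).

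- Standard error: √(0.90 × 0.10 / 30) = √0.003 = 0.0548
- Half-width: 1.96 × 0.0548 = 0.1074
- Limits: 0.90 − 0.1074 = 79.3% and 0.90 + 0.1074 = 100.7%

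Rounded and cut at 100%, this is 79% to 100%, which matches the plan at both ends.

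**Step 2: compute the specified interval.** The Clopper-Pearson limits are beta quantiles.

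- Lower: the 0.025 quantile of Beta(x, n − x + 1) = Beta(27, 4), which is 0.7347
- Upper: the 0.975 quantile of Beta(x + 1, n − x) = Beta(28, 3), which is 0.9789

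The interval is 73.5% to 97.9%.

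**Step 3: size of the difference.**

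| | Plan | Clopper-Pearson, 27/30 | Difference |
|---|---|---|---|
| Lower limit | 79% | 73.5% | 5.5 points too high |
| Upper limit | 100% | 97.9% | 2.1 points too high |
| Width | 21 points | 24.4 points | 3.4 points too narrow |

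**Step 4: check the lower limit directly.** An exact 95% lower limit is the true rate at which 27 or more responders in 30 would occur with probability 2.5%. At a true rate of 73.47% that probability is 2.5%. At 79% it is 9.8%. So 27 of 30 does not exclude 79% at the stated confidence level.

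**Step 5: look for another explanation.** These are other intervals at 27/30, two-sided 95% unless noted.

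| Method | Interval |
|---|---|
| Wald, continuity-corrected | 77.6% to 102.4% |
| Wilson | 74.4% to 96.5% |
| Agresti-Coull | 73.6% to 97.3% |
| Jeffreys | 75.7% to 97.1% |
| Mid-P | 75.1% to 97.4% |
| Logit | 73.2% to 96.7% |
| Arcsine | 77.0% to 98.0% |
| Clopper-Pearson, two-sided 90% | 76.1% to 97.2% |

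None gives 79% to 100%. Applying Clopper-Pearson to the anticipated 94% (28.2 of 30, not a possible count) gives 78.9% to 99.4%. That comes near the lower limit but misses the upper, and the sentence says 90%.

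**Step 6: neighbouring cases by Clopper-Pearson.**

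| Responders | Rate | Interval |
|---|---|---|
| 28/30 | 93.3% | 77.9% to 99.2% |
| 29/30 | 96.7% | 82.8% to 99.9% |
| 30/30 | 100% | 88.4% to 100% |
| 54/60 | 90% | 79.5% to 96.2% |

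At n = 30 the upper limit is 100% only when there are no failures. At a 90% rate, a lower limit of about 79% needs roughly 60 patients, twice the planned number.

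**The case against.** The arithmetic is not in dispute; the case on the other side is that little depends on it. The synopsis does not derive 30 patients from this interval, enrolment is described as up to or approximately 30, and no precision target is set that the corrected figure would miss. There is no performance goal, success threshold or stopping boundary for SVR12. The scheduled reviews with the independent data and safety monitor are triggered by the first 10 subjects and use no rule based on this interval. Because Clopper-Pearson is already the named method, the reported result will be correct if the named method is followed, even if this sentence is never edited.

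All of that stands, and it limits the consequence. It would be wrong to say that the sample size rests on the 79% figure. It does not make the figure right. An incorrect example beside the method statement also leaves room for someone to treat the example as authority for reporting a Wald interval, which performs poorly near 100%, where SVR12 is expected to fall.

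Two smaller points also stand. The documents do not say that Wald was used; that is inferred from the match at both limits. And 28 of 30 (93.3%) lies just below the anticipated rate of above 94%, while the next possible count, 29 of 30, lies above it. Any added example should be labelled accordingly.

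**Conclusion.** The concern holds. For 27 of 30, the specified two-sided 95% Clopper-Pearson interval is 73.5% to 97.9%, not 79% to 100%. Of the intervals tried, only the truncated Wald interval reproduces both stated limits. The conclusion rests only on inputs the plan itself states; the one inference is how the wrong figure arose, and the correction does not depend on it. The sole precision statement for the primary endpoint is wrong and too favourable, so it must be corrected. Estimand, analysis method, enrolment and conduct are unaffected.

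**What to change.** Keep Clopper-Pearson as the analysis method and replace the planning sentence with, for example: *With 30 patients and 27 responders (90%), the two-sided 95% Clopper-Pearson interval is 73% to 98%.*

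As an optional addition rather than a correction, give the interval near the anticipated rate, naming the count: 28 of 30 (93.3%) gives 78% to 99%. Because 94% of 30 is not a whole number, 29 of 30 (96.7%, 83% to 99.9%) can be shown beside it.

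The cost is one sentence, or two with the addition. The stated precision becomes less favourable; no visit, procedure or enrolment number changes.
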